5.9 Costs

There are no costs to the participant and insurance will not be billed.

5.10 Compensation

Participants will be compensated according to NIDA IRP Remuneration Guidelines and following guidelines from NIH OHSRP Policy 302. Participant compensation rates are outlined in the table below.

Abbreviated Title: Mindfulness and Teen Vaping
Version Date: 07/21/2025
NIH IRB#: IRB001855

| | Consent/Study Procedures: Rate = \$20/hr | MRI: Rate = \$25/scan | MBSR (parent/guardian only) | Follow-Ups: Rate = \$20/hr | Estimated TOTAL |
|--------------------------------------|--|------------------------------|------------------------------------|-----------------------------------|------------------------|
| Non-Vaping Participant | Consent/Screening/Baseline/MRI Visit ~5 - 5.5 hrs = ~\$100-\$110 | 1 scan = \$25 | N/A | N/A | ~\$125 - \$135 |
| Non-Vaping Participant Parent | Consent/Screening/Baseline/MRI Visit ~1 - 5.5 hrs = ~\$20 - \$110 | N/A | N/A | N/A | ~\$20 - \$110 |
| Vaping Participant | Consent/Screening/Baseline/MRI Visits ~ 7 - 7.5 hrs = ~\$140-\$150 | 2 scans = \$50 | travel reimbursement only | ~4 hrs = \$80 | ~\$270 - \$280 |
| Vaping Participant Parent | Consent/Screening/Baseline/MRI Visits ~ 1 - 7.5 hrs = ~\$20-\$150 | N/A | travel reimbursement only | ~0-4 hrs = \$0-\$80 | ~\$20 - \$230 |

We anticipate non-vaping participants will earn about \$125 - \$135, while vaping participants will earn about \$270 - \$280, depending on the total time it takes for each participant to complete study procedures. If participants withdraw before completion of the study, they will be compensated only for the time/procedures completed. **Time spent in MBSR training sessions will not be compensated, as there is potential for direct benefit from the MBSR training.**

One parent/guardian must be present for the consent process for participants under 18 y/o and one parent/guardian will be compensated \$20/hr. They will have the option to remain at NIDA while their minor is participating. If so, they will be compensated \$20/hour for their time, except for MBSR training time.

We anticipate a non-vaping participant's parent/guardian will earn up to about \$110 if they stay at NIDA for all of the study procedures.

We expect a vaping participant's parent/guardian will earn up to about \$230 if they attend all visits and remain at NIDA for all procedures. Note that neither parents nor participants are compensated for MBSR training visits due to potential of direct benefit to the teen.

Additionally, travel will be provided or reimbursed for participants. Accompanied minors or participants who are age 18 can be provided a ride share through NIDA or reimbursed for their travel expenses, or given a \$15 flat rate. Unaccompanied minors may be reimbursed for travel costs or provided a \$15 flat rate.

Abbreviated Title: Mindfulness and Teen Vaping

Version Date: 07/21/2025

NIH IRB#: IRB001855

Meals or snacks will be provided during study visits.

Method of Payment: The NIDA IRP has a contractor in place for remuneration. The participant/parent/guardian will generally receive payment earned for that day at the end of each day of participation when possible. If any procedures are completed remotely or during evening or weekend hours, payment may be delayed.

Remuneration will generally be in cash payments. Payment by gift cards (as long as NIDA IRP guidelines permit), check or electronic means (e.g., via PayPal) may also be offered. NIDA IRP has a cash limit per day so the participant/parent/guardian may choose multiple payment methods if they are owed more than the current limit, in one visit. We will coordinate getting any payments due to the participant during regular business hours with the various payment options described above. Payment by check or electronic means (e.g., via PayPal) may also be offered.

6 STUDY INTERVENTION

6.1 Study Interventions(s) or Experimental Manipulations(s) Administration

6.2 Study Intervention or Experimental Manipulation Description

Description of intervention: MBSR Program: The adapted MBSR program is a structured evidence-based 9-week program that consists of eight weekly 2-hour sessions and one 3-hour retreat. We will conduct 4-6 MBSR groups of 8-12 participants each. The program content includes: 1) material related to mindfulness, meditation, yoga, and the mind-body connection; 2) experiential practice of mindful meditation (sitting, lying down, walking, etc.), mindful yoga, and “body scan”, and encouragement of home practice; and 3) group discussion of barriers to effective practice. MBSR group discussions are focused on issues related to the practice of mindfulness in daily life. As with our previous studies, the group will be led by an instructor trained in MBSR, experienced with mindfulness instruction in youth with psychiatric conditions, using the adapted MBSR workbook. MBSR program fidelity will be tracked using a previously developed checklist consisting of the main concepts, content, activities, and qualitative assessment for each class.

6.3 Administration

The MBSR intervention will be delivered in-person or virtually for 9 weeks. Virtual MBSR sessions will be held via videoconference using an NIH Information Systems Security Officer (ISSO) approved teleconference software.

6.4 Fidelity

6.5 Interventionist Training and Tracking

A commercially available MBSR trainer, experienced in working with adolescents in research studies, will deliver the training. Documentation of the conduct of each training session will be provided.

6.6 Measures to Minimize Bias: Randomization and Blinding

N/A

6.7 Study Intervention/Experimental Manipulation Adherence

Abbreviated Title: Mindfulness and Teen Vaping

Version Date: 07/21/2025

NIH IRB#: IRB001855

The trainer(s) will follow a manual in delivering the treatment and document the conduct of each session for review.

6.8 Concomitant Therapy

Participants may use their normal medications, including over-the-counter medications and dietary supplements, and prescribed medications. Medication usage will be assessed at each study visit and documented in the relevant Case Report Form (CRF).

6.9 Rescue Therapy

N/A

7 STUDY INTERVENTION/EXPERIMENTAL MANIPULATION DISCONTINUATION AND PARTICIPANT DISCONTINUATION/WITHDRAWAL

7.1 Discontinuation of Study Intervention/Experimental Manipulation

Participants who engage at any level in the MBSR training and are not disruptive will be allowed to continue with the intervention and the protocol in general. Only those who express a desire to withdraw from the MBSR, persist in disruptive behaviors during sessions, or are lost to follow-up will be discharged from the study. There are no safety endpoints that need follow-up after discontinuation of MBSR or the study.

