4 STUDY DESIGN

4.1 Overall Design

This is natural history study (comparison of vaping to non-vaping adolescents) and an open label pilot study (MBSR intervention to vaping adolescents).

This single-sight study will be carried out at the NIDA-IRP's Biomedical Research Center in Baltimore, MD.

The study will enroll up to 60 nicotine vaping youth and 60 non-vaping youth to obtain complete data on N=40 tobacco vaping youth 13-18 years old and N=40 age, sex, race/ethnicity, SES matched typically developing (TD) non-vaping/non-smoking youth. The study intervention, given to vaping teens, is a Mindfulness-Based Stress Reduction (MBSR) training. The intervention is a group-based instructor-led mindfulness-based stress reduction (MBSR) training.

Abbreviated Title: Mindfulness and Teen Vaping

Version Date: 07/21/2025

NIH IRB#: IRB001855

The MBSR intervention will consist of eight weekly 2-hour sessions and one 3-hour retreat that will take place at the NIDA BRC. Each group will consist of 8-12 participants.

Participants will be recruited online and via our concurrent vaping survey study. Only nicotine vaping youth will participate in the MBSR intervention. The vaping group will participate in one to four primary data gathering visits, all but one of which can be done virtually. The visit that will include the first MRI scan visit must take place in-person 0-3 months pre-MBSR intervention, and the second MRI scan visit will take place 0-6 weeks post-MBSR intervention. The TD non-vaping group will not participate in the MBSR intervention, and therefore will only participate in the baseline assessments (one to four virtual or in-person visits including the first in-person MRI scan). For those receiving the MBSR intervention, there will also be four monthly follow-up visits which may be administered in-person or virtually. The one at the conclusion of MBSR training may be combined with scan 2. The MBSR visits are optional, and as long as one visit is completed, the other visits if missed will not result in a deviation.

We hypothesize that teens who vape will differ from those who do not on all behavioral, cognitive and imaging measures and that the MBSR intervention will alter these measures in the vaping teens so that they will differ less from their non-vaping counterparts.

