7.2 Participant Discontinuation/Withdrawal from the Study

Participants are free to withdraw from participation in the study at any time upon request.

An investigator may discontinue a participant from the study for the following reasons:

- Continual non-compliance (e.g., repeatedly fails to show for scheduled protocol visit (excluding MBSR training sessions) without calling to reschedule, does not complete procedures as instructed, persistent disruptive behavior during MBSR training sessions, etc.)
- Lost-to-follow-up; unable to contact subject (see [Section 7.3, Lost to Follow-Up](#)).
- Any event or medical condition or situation occurs such that continued collection of follow-up study data would not be in the best interest of the participant or might require an additional treatment that would confound the interpretation of the study.
- The participant meets an exclusion criterion (either newly developed or not previously recognized) that precludes further study participation.
- Screen failure
- The individual no longer wishes to participate.

The reason for participant discontinuation or withdrawal from the study will be documented in the participant's electronic research record.

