7.3 Lost to Follow-up

A participant will be considered lost to follow-up if he or she fails to return for MBSR intervention sessions, or any scheduled protocol visit and is unable to be contacted by the study staff.

Abbreviated Title: Mindfulness and Teen Vaping

Version Date: 07/21/2025

NIH IRB#: IRB001855

The following actions must be taken if a participant fails to return to the clinic for a required study visit:

- Study staff will attempt to contact the participant and reschedule a missed follow-up visit within 2 weeks.
- Before a participant is deemed lost to follow-up, the investigator or designee will make every effort to regain contact with the participant (where possible, 3 telephone calls and, if necessary, a certified letter to the participant's last known mailing address or local equivalent methods). These contact attempts should be documented in the participant's medical record or study file.
- Should the participant continue to be unreachable, he or she will be considered to have withdrawn from the study with a primary reason of lost to follow-up.

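### Section 7.1 ends outcome collection for a vaping teen who openly asks to stop MBSR, while a reachable teen who attends once and silently stops is kept and analysed

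*Combined protocol and SAP*

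**What the plan says.** Section 7.1 concerns discontinuing the intervention, but its consequence is leaving the study. Teens who engage with MBSR to any degree and are not disruptive may carry on. It then names those who must leave the study as a whole: "Only those who express a desire to withdraw from the MBSR, persist in disruptive behaviors during sessions, or are lost to follow-up will be discharged". Its only remark on what follows is "There are no safety endpoints that need follow-up after discontinuation of MBSR or the study". Imaging and behavioural outcomes are not mentioned.

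The other sections protect a teen who simply stops coming:

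- Section 4.1: "The MBSR visits are optional, and as long as one visit is completed, the other visits if missed will not result in a deviation".
- Section 7.2 lists repeated no-shows as non-compliance but carves out MBSR: "excluding MBSR training sessions".
- Section 7.3 counts a teen who stops attending as lost only if the teen also "and is unable to be contacted by the study staff".
- Section 9.3 defines a modified intention-to-treat set. The pre-post imaging comparison takes vaping teens who completed the intervention, however many sessions they attended, and who have both scans. The vaping and related outcomes also need at least one follow-up visit.

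On disruption, 7.2 is softer than 7.1. It lists "persistent disruptive behavior during MBSR training sessions" under the lead-in "An investigator may discontinue a participant from the study for the following reasons".

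On numbers, section 4.1 says: "The study will enroll up to 60 nicotine vaping youth and 60 non-vaping youth to obtain complete data on N=40 tobacco vaping youth".

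**The concern.** Stopping an intervention and leaving a study are different events, and 7.1 merges them. Two teens with the same exposure, one session each, are handled differently because one of them told the staff. The first loses scan 2 and all follow-up; the second is assessed and analysed.

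The affected group is narrow: teens who openly stop MBSR, or are removed from it, but would still have come to assessments. For them the protocol itself creates the missing data, and the trigger is rejection of the treatment under study.

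This bears on Primary Endpoint 2 and on the vaping and behavioural change measures. All are uncontrolled pre-post comparisons, and section 9 describes no missing-data method. Enrolling up to 60 to obtain 40 complete restores the count but not the make-up of the set. The baseline comparison with non-vaping teens is not touched, since 9.3 needs only the first scan for it.

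**Working it through.** **Reading the rules side by side**

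| | Asks to stop MBSR after one session | Attends one session, stays away, reachable |
|---|---|---|
| 7.1 | Discharged from the study | Continues |
| 4.1 | Gives no separate route | Missed sessions are not deviations |
| 7.2 no-show rule | Not reached | MBSR sessions do not count |
| 7.3 | Not reached | Not lost, because contactable |
| Scan 2, Visits 12-15 | Not offered in any section | Scheduled |
| 9.3 | Cannot meet the both-scans condition | Included if both scans are done |

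Section 7.1 does not literally say that data collection stops. That follows from discharge from the study with no schedule for afterwards.

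**Size**

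The plan has no figure to reproduce here: it states neither a discharge rate nor a dropout rate. What follows is an illustration.

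Inputs:
- K = 40 teens analysed (section 4.1 target).
- R = discharged teens who would still have attended (assumed).
- d = difference in mean change between kept and recoverable teens, in SD units (assumed 0.2, 0.5, 0.8).
- One paired t-test, two-sided 5%, 39 df (assumed).

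Scale the change score to mean 0 and SD 1 over all K + R assessable teens, so the null is true for them. Let w = R/(K+R), and let recoverable teens improve less by d. Then:

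- shift in the analysed mean, in size = w × d = d × R/(40+R), towards improvement
- within-group SD = √(1 − w(1−w)d²)
- noncentrality = shift/SD × √40, with the rejection rate from the noncentral t

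Worked case, R = 6 and d = 0.5: w = 6/46 = 0.130; shift = 0.065; SD = √(1 − 0.130 × 0.870 × 0.25) = 0.986; noncentrality = 0.0652/0.9857 × 6.325 = 0.42; rejection = 6.9%.

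Shift in SD units, with the rejection rate under a true null:

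| R | w | d = 0.2 | d = 0.5 | d = 0.8 |
|---|---|---|---|---|
| 1 | 0.024 | 0.005 (5.0%) | 0.012 (5.1%) | 0.020 (5.2%) |
| 3 | 0.070 | 0.014 (5.1%) | 0.035 (5.5%) | 0.056 (6.4%) |
| 6 | 0.130 | 0.026 (5.3%) | 0.065 (6.9%) | 0.104 (10.3%) |
| 10 | 0.200 | 0.040 (5.7%) | 0.100 (9.7%) | 0.160 (18.1%) |
| 20 | 0.333 | 0.067 (7.0%) | 0.167 (18.5%) | 0.267 (42.7%) |

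R = 3 would arise if 6 of 60 openly stopped and half would still attend; R = 6 if 12 of 60 did. At d = 0.5, a shift of 0.1 SD needs R = 10, since 0.5 × 10/50 = 0.1. The last row is a ceiling: 60 − 40 = 20 losses from all causes, so w is at most 1/3. It requires every loss to come from this rule and to be recoverable, which is not realistic. At d = 0 the shift is zero; if recoverable teens improve more, its sign reverses. A simulation of 40,000 trials per cell for R = 1, 6, 10 and 20 agreed to within 0.3 percentage points.

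**The case against.** **The effect is small and the inputs are assumed.** The standard error of a 40-person mean change is 1/√40 = 0.158 SD, so a shift of 0.01 to 0.07 SD is under half a standard error. This stands, and it limits how much weight the point can carry.

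**A teen can already stop and stay.** After one session the rest are optional, and staff can say so. True, but this helps only teens who do not ask to withdraw. It leaves the outcome of a candid request to how it is phrased and handled.

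**Section 5.6 makes agreement to MBSR a condition for the vaping group, and 4.4 defines completion as all nine weeks.** Section 5.6 concerns agreement on joining. Section 4.4 defines study completion, not the analysis set. Neither requires later outcomes to go uncollected.

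**The set is labelled modified, and the aim is mechanistic, so adding teens who rejected training dilutes the signal.** The dilution is real. Suppose the kept teens' effect is 0.45 SD and six added teens have zero change. The mean becomes 0.45 × 40/46 = 0.391, the SD 1.011 and n 46, and power falls from about 79% to 73%. But 9.3 already accepts dilution, since it includes teens regardless of attendance. A set that admits one-session silent stoppers and omits one-session open stoppers is not a clean per-protocol set either.

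**The 5% rejection rates do not describe the voxelwise analysis.** Correct. At p < 0.002, which section 9.2 treats as closer to cluster correction, R = 6 and d = 0.5 give about 0.38% pointwise. The 5% figures fit single behavioural or dynamic-connectivity tests.

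**On disruption, 7.2 says only that discharge may happen.** Also correct. The two sections differ, and loss is mandatory only on the wording of 7.1.

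**Conclusion.** The concern holds. As written, the protocol ends outcome collection for teens who openly stop MBSR and keeps equally exposed teens who stop silently, and no section gives the first group a way to remain under assessment. This sits poorly with an analysis set that disregards the number of sessions attended.

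The consequence is probably small: about 0.01 to 0.07 SD for one to six recoverable teens at an assumed 0.5 SD difference, with a single 5% test rejecting a true null 5.1% to 6.9% of the time. The theoretical limit is d/3. These figures rest on assumed values of R and d, and the documents establish neither the size nor the direction of any bias. It is a recommended improvement, not a flaw that undermines the pilot. Its main justification is that the loss is avoidable and that outcomes not collected on schedule cannot be recovered later.

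**What to change.** - **Sections 7.1 and 7.2:** make a request to stop MBSR, or disruption in sessions, a reason to end MBSR only. Continue to invite the teen to scan 2 and Visits 12-15 unless the teen or a parent withdraws from assessments. Record the date and reason for stopping MBSR; 7.2 now documents a reason only for leaving the study.
- **Section 9.3:** replace the condition of having completed the intervention with inclusion irrespective of attendance and of whether MBSR was stopped early. Otherwise a teen who stopped but has both scans could still be excluded. Keep the both-scans and follow-up-visit requirements, and add no one-session minimum.

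The cost is a wording amendment and some extra scheduling of visits already planned for this group. Recovery will be partial, because some teens will decline, and some dilution of the pre-post contrast is possible. A teen who stops MBSR but attends assessments could also count as retained towards the 75% criterion in 9.4.3, at 1/60 = 1.7 percentage points each with 60 enrolled. MBSR stops should therefore be reported separately from study retention.

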7.2 Participant Discontinuation/Withdrawal from the Study

Participants are free to withdraw from participation in the study at any time upon request.

An investigator may discontinue a participant from the study for the following reasons:

- Continual non-compliance (e.g., repeatedly fails to show for scheduled protocol visit (excluding MBSR training sessions) without calling to reschedule, does not complete procedures as instructed, persistent disruptive behavior during MBSR training sessions, etc.)
- Lost-to-follow-up; unable to contact subject (see [Section 7.3, Lost to Follow-Up](#)).
- Any event or medical condition or situation occurs such that continued collection of follow-up study data would not be in the best interest of the participant or might require an additional treatment that would confound the interpretation of the study.
- The participant meets an exclusion criterion (either newly developed or not previously recognized) that precludes further study participation.
- Screen failure
- The individual no longer wishes to participate.

The reason for participant discontinuation or withdrawal from the study will be documented in the participant's electronic research record.

7.3 Lost to Follow-up

A participant will be considered lost to follow-up if he or she fails to return for MBSR intervention sessions, or any scheduled protocol visit and is unable to be contacted by the study staff.

Abbreviated Title: Mindfulness and Teen Vaping

Version Date: 07/21/2025

NIH IRB#: IRB001855

The following actions must be taken if a participant fails to return to the clinic for a required study visit:

- Study staff will attempt to contact the participant and reschedule a missed follow-up visit within 2 weeks.
- Before a participant is deemed lost to follow-up, the investigator or designee will make every effort to regain contact with the participant (where possible, 3 telephone calls and, if necessary, a certified letter to the participant's last known mailing address or local equivalent methods). These contact attempts should be documented in the participant's medical record or study file.
- Should the participant continue to be unreachable, he or she will be considered to have withdrawn from the study with a primary reason of lost to follow-up.

8 STUDY ASSESSMENTS AND PROCEDURES

8.1 Screening Procedures

8.1.1 Screening activities performed prior to obtaining informed consent

A phone screen or online screener (see attached Phone Screen and Online Screening Survey) will be completed with the potential participant to preliminarily ascertain suitability for the study. Screening questions will cover participants' clinical history, which comprises current substance use, including nicotine vaping, contraindications to MRI scanning, general health and mental health, including all regular medications, access to a smartphone and ability to participate in weekly MBSR training sessions (vaping group only). A waiver of consent is requested for the online screening survey and phone screen – please see section 10.

8.1.2 Screening activities performed after a consent for screening has been signed

At the first visit, after consent/assent is obtained, the following measures will be gathered to further assess eligibility for the study:

Diagnostic Assessment (~1.5 hours)

- a. Clinical history – clinician review
- b. Mini International Neuropsychiatric Interview for Children and Adolescents-DSM-5.0 version (MINI-KID-5) or SCID-RV
- c. MRI Safety Assessment
- a. Substance Use History
 - General Substance Use History Questionnaire (with tobacco & e-cigarette smoking, alcohol, and cannabis questions included)
 - Cannabis Use Disorder Test (CUDIT, 8 items, ~1-2 min)

8.2 Study Evaluations & Procedures after eligibility has been determined.

Administration of questionnaires, interviews, or other instruments (Table 1).

Abbreviated Title: Mindfulness and Teen Vaping

Version Date: 07/21/2025

NIH IRB#: IRB001855

The consent, screening activities listed in 8.1.2, and the baseline assessments listed below may be completed in the same visit virtually or in-person, and all or some of these procedures may also be completed in the same visit as the first scan session. Some questionnaires may be completed virtually in between the consent appointment and Scan Day 1.

Orientation and Initial Baseline Assessments (Visit(s) 1, may be conducted virtually) (~35-55 min):

Demographics and Puberty (~2-5min)

- a. Demographics questionnaire
- b. Pubertal Development Scale

Substance Use Measures

- a. General Substance Use (all participants)
 - Timeline Follow-back (TLFB)
 - Past 28-days tobacco vaping (vaping days and vapes or puffs/day), tobacco smoking, cannabis, alcohol, other drugs if relevant. 7-day TLFB for later visits for vaping teens.
 - Craving Questionnaire (~1-5 min)
- b. E-Cigarette Measures (Vapers only)
 - E-cigarette Dependence Scale (EDS, 4 items, 1 min)
 - Nicotine Social Influence Questionnaire (NSIQ, 1 min)
 - Social influence - peer and family e-cigarette use and approval
 - Modified E-Cigarette Fagerstrom Test for Nicotine Dependence (FTND, 8 items, 1-2 min)

Psychological Measures

- Sensitivity to Reward and Sensitivity to Punishment Questionnaire (SRSPQ, 48 items, 5 min)
- Patient Health Questionnaire-9 (PHQ-9, 9 items, 2 min)
 - Assesses degree of depression severity
- General Anxiety Disorder-7 (GAD-7, 7 items, 2 min)
- Difficulty in Emotion Regulation Scale (36 items, 4 min)
- 5-trial Adjusting Delay Discounting Task (bench, 2 min)
 - Assesses discounting of future rewards compared to current rewards
- Momentary Impulsivity Scale (4 items, 1 min)

Mindfulness Measures

- Five-Facet Mindfulness Questionnaire (FFMQ, 39 items, 3 min)

Cognitive Measures

- Digit Span Assessment (forwards and backwards) (DGS, ~3-5 min)

MBSR

Abbreviated Title: Mindfulness and Teen Vaping

Version Date: 07/21/2025

NIH IRB#: IRB001855

The study intervention, given to vaping teens, is a Mindfulness-Based Stress Reduction (MBSR) training. The intervention is a group-based instructor-led mindfulness-based stress reduction (MBSR) training. See section 4 for details related to MBSR training.

MRI Sessions (~2 hours):

Radiographic or other imaging assessments (Visits 1 and 11 for vaping participants; Visit 1 only for controls)

MRI Data Acquisition

The study may use the 3T MRI with custom pulse sequences and image reconstruction and analysis software (via CRADA with Siemens using sequences developed at various universities). All sequences are within FDA approved specific absorption radiation (SAR) limits. We believe this study is a non-significant risk (NSR) device study subject to the abbreviated IDE requirements of 21 CFR 812.2(b). The devices (custom pulse sequences and image reconstruction and analysis software), as used in this study, do not meet the definition of a significant risk (SR) device per 21 CFR 812.3(m) because:

1. It is not intended as an implant and presenting a potential for serious risk to the health, safety, or welfare of a subject because the MRI is not an implant.
2. It will not be used in supporting or sustaining human life and does not present a potential for serious risk to the health, safety, or welfare of a subject because MRI will not be used in supporting or sustaining human life.
3. It will not be for a use of substantial importance in diagnosing, curing, mitigating, or treating disease, or otherwise preventing impairment of human health and presenting a potential for serious risk to the health, safety, or welfare of a subject because the MRI results will not be used to provide clinically relevant information for participants.
4. It does not otherwise present a potential for serious risk to the health, safety, or welfare of a subject because the pulse sequences and image reconstruction and analysis software are used within the FDA approved SAR limits.

Per regulations, abbreviated IDEs (NSR device studies) do not require an application to the FDA as the IRB acts as FDA's surrogate for review, approval, and continuing review of these type of device studies.

At scan visits:

- Participants will present to the NIDA-IRP BRC for a medical update, and an MRI safety screen, conducted by the MAI/designee or research nurse. They will also complete a nursing evaluation (weight, urine drug test, urine pregnancy test, urine cotinine test, breath CO, and ALC test), and will orient to the MRI scanner. Participants will then undergo a ~60 min MRI session on a Siemens 3.0T MRI scanner using a 32-channel head coil.
- Participants will be instructed to abstain from cannabis, alcohol, and other drugs for 24 hours and limit caffeine for 12 hours prior to scan visits. They will be instructed to continue

Abbreviated Title: Mindfulness and Teen Vaping

Version Date: 07/21/2025

NIH IRB#: IRB001855

nicotine products as usual. Abstinence will be verified on scan days via self-report, and UDT (listed above), with participants rescheduled if they test positive for drugs on UDT and have signs of acute intoxication (per clinical assessment).

- Scan sessions will include: (1) anatomical MRI for registration (T1W), (2) resting-state scan (whole-brain T2*w gradient-echo EPI sequence) [10 minutes, eyes-open, fixation cross], (3) Diffusion Tensor Imaging (DTI).

Follow-up Assessments

Within three weeks of the MBSR training completion, vaping participants will complete substance use questionnaires, psychological assessments, mindfulness measures, and cognitive assessments in-person or via secure video call. Our goal is to complete both scan 2 and the initial post-MBSR training assessments within about 1 week after MBSR training. This first follow up visit may be combined with the post MBSR scan 2 but scan 2 may take place as late as approximately 6 weeks after MBSR training to accommodate scheduling. Participants will then have three more follow-up visits, approximately a month apart, in which they complete the measures listed above. These three monthly visits will be dated from the completion of the first assessments following MBSR training (not the scan 2 date). Note: The Digit Span will only be completed at one of the follow up visits, and the FFMQ, DERS and SRSPQ will be completed during two of the visits, preferably the first and the last. The Delayed Discounting questionnaire will only be completed if the follow up visit is in-person. A nursing evaluation consisting of urine sample for a drug test, and breath CO and alcohol test will be taken at each in-person follow-up.

Participants will also engage with the Craving-to-Quit app to elucidate changes in vaping behavior, emotion, and cognition in the 3 months following the MBSR training. The follow-up visits will take about 1 hour each to complete.

